10. STUDY DRUG

10.1. Study drug regimens

Overview DeTACT drug regimens	
TACT-arm	ACT-arm
In all sites	
Artemether -lumefantrine x 3 days PLUS Amodiaquine x 3 days	Artemether -lumefantrine x 3 days PLUS Placebo x 3 days
In all sites except Rwanda	
Artesunate -mefloquine x 3 days PLUS Piperaquine x 3 days	Artesunate -mefloquine x 3 days PLUS Placebo x 3 days
In low transmission settings subjects will receive a single low dose primaquine on day 1 according to the WHO guidelines and local regulations	

Subjects will be treated with weight-based doses according to the schedule in appendix 2.

The study drugs will be administered by study medical or nursing staff while the subjects are hospitalised.

The study drugs containing artemether-lumefantrine+/-placebo will be taken with at least 1.2 grams of fat to optimize absorption (comparable to 80-100 ml of a MILO milk carton or an equivalent fat containing beverage or snack).

No meals or snacks must be consumed for 1 hour before and after intake of study drugs containing artesunate-mefloquine+/-piperaquine. In case any food is taken, it must be non-fatty snacks (e.g., small quantity of rice, bread, crackers, etc.)

10.2. Drug administration procedures in case of vomiting

If the patient vomits within half an hour after intake of the antimalarial drugs, the dose will be repeated. If vomiting occurs between half and one hour, half of the dose will be repeated. If vomiting occurs more than one hour after drug administration, no repeat dosing will be done. Repeat doses will be recorded on the CRF. If vomiting within 1 hour occurs more than one time,

no repeat dosing is allowed. In this case the patient will be treated at the discretion of the investigator, for instance with intravenous artesunate.

10.3. Treatment in case of a recurrent infection

Subjects with persistent asexual parasitaemia on day 7 or who develop a recurrent parasitaemia after day 7 with no signs of severity will be treated with either an ACT or a different combination e.g. quinine and doxycycline or clindamycin, in accordance with local recommendations.

Subjects who develop a non-falciparum parasitaemia during follow up will be treated according to local guidelines or recommendations.

10.4. Rescue treatment

The indication for rescue treatment is:

- The development of any danger signs or signs of severe malaria at any point.

Rescue treatment will consist of parenteral artesunate (per WHO Treatment Guidelines, 3rd edition, 2015) as below:

- For subjects <20 kg bodyweight, 3 mg/kg IV/IM STAT, followed by 3 mg/kg IV/IM at 12 hours and 24 hours and then daily until able to take oral medication
- For subjects ≥ 20 kg bodyweight, 2.4 mg/kg IV/IM STAT, followed by 2.4 mg/kg IV/IM at 12 hours and 24 hours and then daily until able to take oral medication.

If needed, the rescue treatment will be adjusted to local guidelines.

10.5. Concomitant medication

Throughout the study, investigators may prescribe concomitant medications or treatments deemed necessary (e.g. antipyretics or anti-emetics) to provide adequate supportive care except for antibiotics with antimalarial activity unless unavoidable (e.g. doxycycline, azithromycin). If these are required the subjects will be kept in the study and this will be noted as a protocol deviation. Anti-emetics should not be prescribed as a prophylaxis if no nausea or vomiting is present.

If anti-emetics are indicated metoclopramide is the preferred anti-emetic as this drug has the least QTc-interval prolonging effect of the anti-emetics that are commonly prescribed.

Antimalarials for recurrent infections and non-falciparum malaria will be prescribed as described above. Any medication, other than the study medication taken during the study will be recorded in the CRF.

10.6. Study drug details

In the first year the Triple ACTs will consist out of co-blistered or co-packaged combinations of an ACT and a matching partner drug. If healthy volunteer studies comparing co-blistered/co-

packaged and co-formulated formulations of Triple ACTs prove bioequivalence of all drugs the Triple ACT arms will be changed if possible to co-formulated formulations in the second year.

10.6.1. Artemether-lumefantrine

Currently available as dispersible tablets containing 20 mg of artemether and 120 mg of lumefantrine, in a fixed-dose combination formulation. The flavoured dispersible tablet paediatric formulation facilitates use in young children.

Target dose/range:

The dose of artemether-lumefantrine is administered according to the treatment schedule in appendix 2, thereby approaching the WHO-recommended target ranges of artemether 5-24 mg/kg and lumefantrine 29-144 mg/kg over 3 days.

10.6.2. Amodiaquine

Amodiaquine is available as dispersible tablets of 40 mg. The weight-based treatment schedule in appendix 2 aims for a dosage of approximately 10mg (4.5-15mg)/kg/day amodiaquine for three days.

10.6.3. Artesunate

Artesunate will be administered according to an optimised dosing schedule using tablets of 32 or 100 mg artesunate with a dosing target of 4 mg/kg/day (see dosing schedule in Appendix 2).

10.6.4. Mefloquine

Mefloquine will be administered according to an optimised dosing schedule using tablets of 70 or 220 mg mefloquine hydrochloride with a dosing target of 8.3 mg/kg/day (see dosing schedule in Appendix 2).

10.6.5. Piperaquine

Piperaquine will be administered according to an optimised dosing schedule using tablets of 160 or 500 mg of piperaquine tetraphosphate. The weight-based treatment schedule in appendix 2 aims for a dosage of approximately

- 24 mg/kg/day in patients <25 kg (range 16.0 – 32.0 mg/kg) piperaquine for three days, thereby approaching the WHO-recommended target range of 20 – 32 mg/kg per day.
- 18 mg/kg/day in patients ≥25 kg (range 15.0 – 29.4 mg/kg) piperaquine for three days, thereby approaching the WHO-recommended target range of 16 – 27 mg/kg per day.

10.6.6. Primaquine

Primaquine is available in tablets of 7.5 and 15 base mg. The weight-based treatment schedule in appendix 2 aims for a dosage of approximately 0.15-0.375 mg/kg on day one thereby approaching the 0.25 mg base/kg single dose recommended by the WHO.

10.6.7. Placebo for piperazine

Placebo tablets for piperazine are currently under development. They will be identical in size, shape and colour. We aim for a similar taste of piperazine and the placebo.

10.6.8. Placebo for amodiaquine

Placebo tablets for amodiaquine are currently under development. They will be identical in size, shape and colour. We aim for a similar taste of amodiaquine and the placebo.

10.7. Storage of study drugs

All efforts will be made to store the study drugs in accordance with the manufacturers' recommendations in a secure area. This may be difficult at some sites where air-conditioned storage rooms are not available. The study drugs should be stored between 15°C to 30°C (59°F to 86°F).

In case of doubts on storage conditions meeting the recommendations the artemisinin-derivatives and partner drug content of batches of ACTs and TACTs will be retested at the end of the study.

10.8. Accountability of the study drugs

All movements of study medication will be recorded. Both study medication of individual patient and overall drug accountability records will be kept up to date by the study staff.

11. DISCONTINUATION/ WITHDRAWAL OF PARTICIPANTS FROM THE STUDY

Each participant has the right to discontinue the study drug or withdraw from the study at any time. Data accrued up until the time of discontinuation/withdrawal will be used in the analysis, unless the subject wishes to withdraw even the data which has already been collected in which case those data will be excluded as well.

In general, the investigator must make every effort to perform the study procedure until day 63.

In principle the following situations are NOT reasons to discontinue the patient from the study:

- Significant non-compliance with treatment regimen or study requirements
- An adverse event which requires discontinuation of the study medication or results in inability to continue to comply with study procedures

- Disease progression which requires discontinuation of the study medication or results in inability to continue to comply with study procedures
- Development of severe malaria
- Recurrent parasitaemia
- Loss to follow up (every attempt should be made to re-contact the participant)
- Discontinuation of the study drug

However, the investigator may discontinue participation in the study of a participant if he or she considers it necessary.

In addition, the participants always have the right to withdraw consent in writing or verbally.

The reason for withdrawal or discontinuation, if available, will be recorded in the CRF. If the study drug or participation in the study is discontinued due to an adverse event, the investigator will arrange for follow-up visits at least until the adverse event has resolved or stabilised.

Any pregnancy must be reported to the Principal Investigator within one working day of awareness. The PI must take all reasonable efforts to discover the outcome of the pregnancy and fill out the pregnancy form. If there is a congenital abnormality or a still born baby, this needs to be reported as a serious adverse event.

12. SAFETY REPORTING

This trial will use drugs that have either been registered or evaluated extensively.

To allow for comparison of safety and tolerability of both new TACTs compared to the ACTs we will record and review all Adverse Events (AEs) and Serious Adverse Events, (SAEs) that occur in the study.

A symptom questionnaire will be performed daily during hospitalisation and at each subsequent visit to the health care facility, to aid in the identification of adverse events. An additional questionnaire will be administered to subjects who report psychological symptoms.

The investigator is responsible for the detection and documentation of events meeting the criteria and definition of an adverse event (AE) or serious adverse event (SAE), as provided in this protocol.

All SAEs and AEs will be promptly documented from the moment of randomisation in the study to discontinuation of the patient from study participation. Any events occurring between screening and randomization will be considered as baseline, pre-existing conditions. Any conditions that were present at baseline will not be considered adverse events unless the grade of the condition deteriorates.

Each adverse event will be graded according Common Terminology Criteria for Adverse Events

(CTCAE) version 5.0, adapted for paediatric populations where needed:

https://ctep.cancer.gov/protocolDevelopment/electronic_applications/ctc.htm#ctc_50

All adverse events must be recorded in the AE /SAE CRF. To avoid colloquial expressions, the adverse event should be reported in standard medical terminology. If a definitive diagnosis is possible, then it should be recorded. Whenever possible, the aetiology of the abnormal findings will be documented on the CRF. Any additional relevant laboratory results obtained by the Investigator during the course of this study will be recorded on the CRF.

If the event meets the criteria for “serious”, the SAE must be reported to the safety team within 24 hours from the time that the event was identified. The safety team will consist out of the Principal investigator, the study coordinator, a representative of the CTSG and the Medical Monitor. If further data is required, additional documentation can be submitted, but an initial report should be submitted within the timeframe. All SAEs must be followed until resolution, or until the SAE is deemed permanent or leads to death. SAEs must also be reported to the ECs and the Regulatory Authorities as per required by local guidelines.

12.1. Definitions

12.1.1. Adverse events (AEs)

An AE is any undesirable event or clinical deterioration that occurs to a study participant during the course of the study; that is, from the time of administration of study drugs until study ends (i.e., until the follow up visit) whether or not that event is considered related to the study drugs, or to a concomitant drug or procedure, e.g.:

- any unfavourable and unintended symptom
- physical sign
- abnormal laboratory result
- an illness
- any pre-existing condition that has worsened in grade

Any new clinical sign or clinical deterioration that occurs between signing the consent form and the administration of study drugs is not an AE. This information will be recorded in the medical records, as a pre-existing condition.

12.1.2. Grading of laboratory abnormalities

Basic biochemical assessments of markers related to hepatic and renal toxicity will be performed on day 0 (baseline) day 3, day 7 and 28.

In addition haemoglobin, platelet counts, white blood cell counts and white blood cell differentiation will be obtained at day 0, day 3, day 7 and day 28.

If found to be abnormal the values will be graded according to the CTCAE table and followed up until resolved or deemed to be permanent.

12.1.3. Serious adverse events (SAEs)

A serious adverse event is an AE that:

- results in death
- is life-threatening i.e. the patient was at risk of death at the time of the AE
- requires inpatient hospitalisation or prolongation of existing hospitalisation
- results in persistent or significant disability/incapacity
- is a congenital anomaly/birth defect
- Any other significant medical condition

More than one of the above criteria can be applicable to the one event. Other significant medical conditions may be considered an SAE when, based upon appropriate medical judgment, they may jeopardize the patient or require medical or surgical intervention to prevent one of the outcomes listed in the definition above. Examples of such medical events include allergic bronchospasm requiring intensive treatment in an emergency room or at home, blood dyscrasias or convulsions that do not result in hospitalisation, or development of drug dependency or drug abuse.

12.1.4. Study defined SAEs

For the purpose of this study, the following are considered SAEs

- Prolongation of the QT or QTc interval to >500 milliseconds
- AST/ALT >10 times ULN
- ALT or AST >3 times ULN with Total Bilirubin >2 times ULN (Hy's Law)
- Creatinine >3.5 times ULN

12.2. Reporting procedures for Serious Adverse events

All SAEs must be reported by the site investigator within one day of his or her awareness of the SAE to the Study PI, Study Coordinators, Medical Monitor and the CTSG by faxing or emailing the CRF documenting the SAE. ([contact]; email: [contact]).

Further reports should be submitted, if required, until the SAE is resolved, is deemed permanent or results in death.

The site investigator must also report the SAEs to the local ethics committee and the regulatory authority in accordance with local requirements.

12.3. Evaluating adverse events and Serious adverse events

12.3.1. Assessment of intensity of AE or SAE

Each adverse event will be graded according Common Terminology Criteria for Adverse Events (CTCAE) version 5.0 (adapted for paediatric populations as needed). This will be included in the safety monitoring plan.

If an adverse event is not listed in the CTCAE table, the Investigator will assess the severity using the following guidelines:

- 1 = Mild: asymptomatic or mild symptoms; clinical or diagnostic observations only; intervention not indicated.
- 2 = Moderate: minimal, local or non-invasive intervention indicated; limiting age appropriate instrumental ADL*
- 3 = Severe or medically significant but not immediately life-threatening; hospitalization or prolongation of hospitalization indicated; disabling; limiting self-care ADL**
- 4 = Life-Threatening consequences; urgent intervention indicated
- 5 = Death related to AE

Activities of Daily Living (ADL)

*Age-appropriate instrumental ADL which will be defined in study SOPs.

**Age-appropriate self-care ADL which will be defined in study SOPs.

12.3.2. Assessment of relatedness of AE or SAE to study drugs

The investigator is obligated to assess the relationship between study drug and the occurrence of each AE/SAE using the following categories of relatedness:

- Definite: clear-cut temporal association
- Probable: clear-cut temporal association, with improvement upon drug withdrawal, and not reasonably explained by the patient's known clinical state or other aetiology.
- Possible: less clear temporal association; other aetiologies are possible. (Other possible aetiologies should be recorded on the CRF).
- Not related: no temporal association with the study drug; assessed as related to other aetiologies such as concomitant medications or conditions, or patient's known clinical state.

The investigator will provide the assessment of causality as per the AE/SAE case record form.

12.3.3. Outcome of AE and SAEs

The investigator will follow-up the AE and SAE until resolution, death, deemed permanent and no further medically relevant information can be expected. AE and SAE outcome will be classified as follows:

- Continuing/ongoing
- Resolved

- Resolved with sequelae
- Permanent
- Fatal

12.4. Clarification of the difference in the meaning of ‘severe’ and ‘serious’

The term “severe” is often used to describe the intensity (severity) of a specific event (as in mild, moderate, or severe myocardial infarction); the event itself, however, may be of relatively minor medical significance (such as severe headache). This is not the same as “serious”, which is based on the outcome or criteria defined under the serious adverse event definition and the defined study specific SAEs. An event can be considered serious without being severe if it conforms to the seriousness criteria, similarly severe events that do not conform to the criteria are not necessarily serious. Seriousness (not severity) serves as a guide for defining regulatory reporting obligations.

13. SOURCE DATA

Source documents are original documents, data, and records from which participants’ CRF data are obtained. These include, but are not limited to, hospital records (from which medical history and previous and concurrent medication may be summarised into the CRF), clinical and office charts, laboratory and pharmacy records, diaries, microfiches, radiographs, and CRFs.

CRF entries will be considered source data if the CRF is the site of the original recording (e.g., there is no other written or electronic record of data). In this study, the CRF will be used as the source document for most of the data points.

14. LABORATORY STUDIES

14.1. Drugs concentration assays

Antimalarial drug concentrations will be measured in plasma samples at the end of the study period or earlier if requested, for instance by the DSMB. All assays will be performed using validated LC-MS/MS methodologies at the Department of Clinical Pharmacology, MORU, Bangkok, Thailand. Observed antimalarial drug measurements will be used for initial statistical analyses and group comparisons to assess potential drug-drug interactions between drugs, relationship between drug concentrations and safety parameters, and relationship between drug concentrations and efficacy parameters.

All collected PK samples will also be analysed using nonlinear mixed-effects modelling to assess the possible drug-drug interactions and the relationship between drug concentrations and treatment outcomes (i.e. safety and efficacy outcomes). Individually predicted drug levels at the time of QTc-measurements will also be used to evaluate a direct relationship between possible QTc-prolongation and drug exposures.

14.2. Ex vivo and in vitro sensitivity assays

Ex vivo and *in vitro* assays will be performed to measure parasite responses to artemisinin derivatives and partner drugs according to the latest standards at the time of assessment. Parasites will also be cryopreserved for future studies.

14.3. Molecular studies

Parasite DNA will be used for genetic studies including but not limited to microsatellite typing and single nucleotide polymorphisms (SNP) typing whole genome sequencing to identify parasite clones, to measure proportions of parasites carrying mutations of functional and/or operational relevance (genetic markers associated with drug resistance, complete or partial deletions in *pfhrp2* gene), to generate data for genome-wide association studies with *in vivo*, *ex vivo*, and *in vitro* responses of parasites to artemisinin and controls. Further, the genotype data from different sample types will be compared to develop methods for sample collection methods adapted to resource-poor settings.

Parasite RNA will be used for transcriptome analyses and for RNA-based detection, characterization and/or quantitation of gametocytes.

Blood samples (dried blood blots) for host genotyping will be obtained and stored from all subjects recruited with their consent. Genotyping will be performed on the samples of subjects with suspected abnormal pharmacokinetics or pharmacodynamics (for instance in case of unexpected adverse events such as severe prolongation of the QTc-interval). Potential targets for targeted genotyping are polymorphisms in genes coding for enzymes related to drug metabolism (e.g. cytochrome P450 enzymes) and genes and mutations predisposing to long QT-syndrome such as but not limited to the genes KCNQ1 (LQT1), KCNH2 (LQT2), and SCN5A (LQT3).

14.4. PCR for quantitative parasitaemia

One of the objectives of this study is to measure assess the parasite clearance dynamics by PCR and compare these with clearance rates estimated using this method to microscopy.

14.5. Immunity

On enrolment and in case of recurrent parasitaemia, quantitative assessments for a panel of antibodies against *Plasmodium falciparum* will be performed. Antibody levels will be correlated with markers of disease outcome such as parasite clearance rates, 42 day efficacy and day of recrudescence or reinfection.

15. STATISTICAL CONSIDERATIONS

15.1. Sample size justification

These studies will have a non-inferiority trial design. Each site will be powered for the efficacy endpoint. For the safety and tolerability endpoint, the sample size will be pooled across the study

sites to achieve the desired power of at least 80% to detect rare events.

For sample size calculations, the following assumptions have been used: The expected efficacy of ACTs (AL, ASMQ) in these countries is expected to be approximately 96%. The matching TACT efficacy is assumed to be at least 90% under the null hypothesis of inferiority based on the WHO 90% efficacy threshold. However preliminary TRACII study data suggest that TACTs potentially may have a better efficacy of 1% to 2% higher in favour of TACT (i.e. a conservative 97%-98% efficacy or higher).

A one-sided alpha of 0.025 has been used in sample size calculations as non-inferiority is in one direction. For the efficacy outcome, a sample size of 60 subjects in the ACT plus placebo arms and 120 subjects in the matching TACT would be needed to achieve approximately 80% power to detect a non-inferiority margin difference between the group efficacy of -6%. With an additional 20% to cover for loss to follow up, we would therefore need 72 subjects in ACT plus placebo group and 144 subjects in the matching TACT in each of the sites. Since there will be 4 arms, it means we will need 432 subjects per site with 144 subjects in the two ACT arms combined and 288 subjects in the two TACT arms combined.

The sample sizes are in the ratio of 1:2 for ACT vs TACT to allow us to collect more safety and tolerability data for TACTs, which could be beneficial to both policy makers as well as future malaria patients [26, 27]. With these numbers of recruited subjects in Africa, we will have a power above 80% to detect an increase of the incidence of adverse events from 1 in 100 to 3 in 100 for subjects treated with ACT as compared to the matching TACT, respectively.

For the safety and tolerability endpoints, we will perform a pooled analysis of the data obtained in the DeTACT-Africa and DeTACT-Asia. A total of 1707 subjects in ACT arms (918 and 789 subjects in the AL and ASMQ arms respectively) and 2787 subjects in TACT arms (1494 and 1293 subjects in the AL+AQ and ASMQ+PPQ arms respectively) recruited in both studies combined will allow us to detect increases of rare adverse events from incidences of 1 in 100 subjects to 3 in 100 subjects also with more than 80% power. The sample size calculations were performed using a specialized sample size calculation software, PASS 15.

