2. SYNOPSIS

Study Title	A multi-centre, randomised, controlled non-inferiority trial to compare the efficacy, safety and tolerability of Triple Artemisinin-based Combination Therapies versus first-line ACTs + placebo for the treatment of uncomplicated Plasmodium falciparum malaria in Africa
ACRONYM	DeTACT-Africa
Trial Design	A partially blinded randomised controlled non-inferiority trial comparing the efficacy, tolerability and safety of Triple ACTs artemether-lumefantrine+amodiaquine (AL+AQ) and artesunate-mefloquine+piperavaquine (ASMQ+PPQ) and the ACTs artemether-lumefantrine+placebo (AL+PBO), artesunate-mefloquine+placebo (ASMQ+PBO) (with single-low dose primaquine in some sites) for the treatment of uncomplicated Plasmodium falciparum malaria to assess and compare their efficacy, safety, tolerability.
Trial Participants	Subjects with acute uncomplicated P. falciparum malaria
Sample size	Estimated total sample size up to 3240 subjects recruited at 8 sites in Africa (Burkina Faso, DRC, The Gambia, Guinea, Niger, Nigeria, Rwanda, Tanzania) 
 - In Rwanda only – 216 subjects - All other sites – 432 subjects per site
Inclusion Criteria	
 • Male or female, aged ≥ 6 months to < 12 years (For Gambia, Rwanda sites only: ≥ 6 months) • Ability to take oral medication • Acute uncomplicated P. falciparum mono-infection • Asexual P. falciparum parasitaemia: 1,000/μL to $\leq 10\%$ parasitaemia, determined on a peripheral blood film (At Gambia, Rwanda sites only: For subjects ≥ 12 years – 1000/μL to 200,000/μL) • Fever defined as $\geq 37.5^{\circ}\text{C}$ tympanic temperature or a history of fever within the last 24 hours • Written informed consent by the subject or by the parent/guardian in case of children lower than the age of consent and assent if required (per local regulations) • Willingness and ability of the subjects or parents/guardians to comply with the study protocol for the duration of the study

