7. PROPOSED ACTIVITIES

Subjects will be randomized to up to four arms: artemether-lumefantrine + amodiaquine, artemether-lumefantrine + placebo, artesunate-mefloquine + piperazine and artesunate-mefloquine + placebo. As a contingency measure in case of significant differences in the efficacy or safety of one of the combinations being tested and/or study drug expiry or unavailability, subjects may be randomized to 2 arms with a matching ACT-TACT pair, i.e., with artemether-lumefantrine + placebo or artemether-lumefantrine + amodiaquine OR artesunate-mefloquine + placebo or artesunate-mefloquine + piperazine.

Some sites may randomize between 2 arms only with matching ACT-TACT pairs, i.e., artemether-lumefantrine + placebo or artemether-lumefantrine + amodiaquine OR artesunate-mefloquine + placebo or artesunate-mefloquine + piperazine. In Rwanda, subjects will be randomized between 2 arms consisting of artemether-lumefantrine + placebo or artemether-lumefantrine + amodiaquine.

In the control arms, the ACT will be co-packed with a matched (appearance) placebo.

In lower transmission settings (Annual Parasite Incidence <50 per 1000 population per year) the treatment will include a single 0.25 mg/kg gametocytocidal dose of primaquine as recommended by the WHO for children ≥ 10 kg. All drug administrations will be observed.

Subjects will be treated in an in-patient unit for 3 days and followed up weekly up to D63. Microscopy to detect and quantify malaria parasitaemia will be performed daily (more frequently in patients with parasite density of $>5000/\mu\text{L}$ at inclusion) during hospitalization, at all weekly and unscheduled visits. A physical examination and measurements of vital signs along with a symptom questionnaire for tolerability will be performed and recorded through a standardized method at baseline, daily during admission and weekly during follow up through D42 and at all unscheduled visits. Physical exam, vital sign measurements and assessments of symptoms will be performed on D49, D56, and D63 only for patients who are parasitaemic or those who report fever or other symptoms. Electrocardiographs will be performed during admission (H0, H4, H52 or H64) and day 42 of follow up to assess and compare the effect of ACTs and TACTs antimalarials on QT or QTc intervals.

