15.2.1. Proportions

These will be compared using chi squared or Fisher's exact test, as appropriate. Crude proportions will be calculated with the exact 95% confidence intervals (CI), where relevant.

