15.2.4. Safety analysis

Safety analyses will be based on the whole population that get administered the study drug. Safety and tolerability of TACTs versus ACTs will be assessed by comparing the frequency (%) of adverse events and serious adverse events, with particular attention to abdominal pain, appetite perturbation, biochemical markers of hepatic and renal toxicity and QT interval prolongation, using the Fisher's exact test. Safety data will be presented in tabular and/or graphical format and summarized descriptively. Any clinically relevant abnormalities or values of potential clinical concern will be described. Subjects will be analysed according to an intention to treat and a per protocol method where appropriate.

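### The Africa-only safety power of above 80% (adverse events 1% vs 3%) is not met by the planned Fisher's exact test: about 78% for the AL pair and 71% for the ASMQ pair at two-sided 5%

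*Protocol*

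**What the plan says.** Protocol 15.1 sizes each site for efficacy and then reports, as a consequence of those numbers, that "we will have a power above 80% to detect an increase of the incidence of adverse events". The increase in question is a tripling, with 1% under an ACT and 3% under its matching TACT. SAP 2.2.1 carries the same sentence. The same protocol section sets at least 80% as the desired power for safety, with data pooled over sites.

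The only alpha in that section is tied to efficacy: "A one-sided alpha of 0.025 has been used in sample size calculations as non-inferiority is in one direction". No alpha, sidedness or test is given for the safety power; the software (PASS 15) is the only detail of method.

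The analysis itself is named. Protocol 15.2.4 and SAP 3.4 compare adverse event frequencies "using the Fisher's exact test", in everyone who received study drug. Protocol 15.2.1, on proportions in general, says "These will be compared using chi squared or" Fisher's test.

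Protocol 15.1 then makes a second claim, for DeTACT-Africa and DeTACT-Asia together: the subjects "recruited in both studies combined will allow us to detect increases of rare adverse events" of the same size, again with more than 80% power. SAP 2.2.1 does not include that paragraph.

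**The concern.** The power is quoted without a method, while the test to be used is fixed elsewhere in both documents. With an event rate near 1% and 1:2 allocation, the common power formulas differ by around ten percentage points, so the choice of method decides whether the figure is above or below 80%.

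The claim is also one figure for two unequal comparisons. It concerns each ACT against its matching TACT, and the ASMQ pair is smaller because Rwanda contributes only to the AL pair.

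Collecting safety data on the TACTs is the protocol's stated reason for 1:2 allocation. If an Africa-only report finds no difference in some adverse event, readers will judge that result against the stated power. If the power is overstated, so is the reassurance, most of all for ASMQ+PPQ.

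**Working it through.** **Arm sizes**

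- Protocol 15.1 gives 72 ACT and 144 TACT subjects per pair per site.
- Protocol 2: "Estimated total sample size up to 3240 subjects recruited at 8 sites in Africa", with 216 in Rwanda and 432 at each other site.
- Protocol 7: "In Rwanda, subjects will be randomized between 2 arms", namely AL+PBO and AL+AQ.
- AL pair, 8 sites: 8 × 72 = 576 and 8 × 144 = 1152.
- ASMQ pair, 7 sites: 7 × 72 = 504 and 7 × 144 = 1008.
- Check: 7 × 432 + 216 = 3240.

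The safety population is everyone dosed, so no loss to follow-up is taken off. Rates are p1 = 0.01 (ACT) and p2 = 0.03 (TACT).

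**Reproducing the stated figure**

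Unpooled normal approximation at two-sided 5%: power = Φ(0.02/se − 1.96), with se = √(0.01×0.99/n1 + 0.03×0.97/n2).

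- AL: se = √(0.0099/576 + 0.0291/1152) = 0.006515; 0.02/se = 3.070; Φ(1.110) = 86.6%.
- ASMQ: se = √(0.0099/504 + 0.0291/1008) = 0.006965; 0.02/se = 2.871; Φ(0.912) = 81.9%.

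Both exceed 80%, so the plan's figure can be obtained this way.

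The pooled-variance formula, Φ((0.02 − 1.96·se0)/se), does not give it. Here p̄ = (0.01 + 2×0.03)/3 = 0.02333 and se0 = √(p̄(1−p̄)(1/n1 + 1/n2)).

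- AL: se0 = 0.007704; Φ(0.752) = 77.4%.
- ASMQ: se0 = 0.008236; Φ(0.554) = 71.0%.

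**Power of the tests named in the documents**

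These figures enumerate every pair of binomial counts and add the probabilities of those that reject. The two-sided Fisher p-value sums all tables no more probable than the observed one.

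| Test | AL 576 vs 1152 | ASMQ 504 vs 1008 |
|---|---|---|
| Fisher, two-sided 5% | 77.8% | 70.6% |
| Fisher, one-sided 2.5% | 75.3% | 67.6% |
| Fisher, one-sided 5% | 85.3% | 79.9% |
| Chi-squared, uncorrected, two-sided 5% | 79.4% | 73.6% |
| Unpooled z, two-sided 5% | 85.9% | 81.5% |

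**Why the unpooled test looks stronger**

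With both arms at 1%, the unpooled test at a nominal one-sided 2.5% declares TACT worse 4.5% of the time (AL) and 4.6% (ASMQ). Its two-sided error is 5.8% and 6.0%, against 3.9% and 3.9% for Fisher's test at nominal 5%. Part of its power comes from exceeding its nominal level in the direction of interest, so it is not comparable with Fisher's.

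**Africa and Asia combined**

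With the protocol's sizes, Fisher's test at two-sided 5% gives 92.5% for AL (918 vs 1494) and 88.0% for ASMQ (789 vs 1293). That claim holds.

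**The case against.** The strongest reply is that the sentence never says its 80% refers to Fisher's test, that the figure can be reproduced, and that no safety alpha is given. The claim concerns an increase, so one-sided 5% is a possible reading. Fisher's test then gives 85.3% for AL and 79.9% for ASMQ: one pair passes and the other falls just short. This stands as a limit, and the shortfall must be quoted with its alpha. But neither document states one-sided 5% for safety, it is looser than the only alpha in Protocol 15.1, and even then the claim is not met in both pairs.

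A second reply is that the combined Africa and Asia analysis is well powered, and that all ACT against all TACT in Africa (1080 vs 2160) would have 97.2%. The first part is right for the protocol, but a reader of SAP 2.2.1 does not see that analysis. The second is a different comparison, because the sentence is about matching pairs.

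A third is that the gap is modest. With Fisher's test at two-sided 5%, power passes 80% at 1% vs 3.1% for AL (81.3%) and 1% vs 3.3% for ASMQ (81.0%). Safety power did not set the sample size, and no stopping or success rule depends on it. All of this is true. It limits the consequence to an accurate statement of power.

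**Conclusion.** The concern holds. With full enrolment and rates of 1% and 3%, Fisher's exact test at two-sided 5% has 77.8% power in the AL pair and 70.6% in the ASMQ pair, against a stated figure above 80%. The chi-squared alternative does not reach 80% in either pair at that level. The chance of missing the increase is 22.2% and 29.4%, where the text implies less than 20%.

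The AL shortfall is small, about 2 percentage points; the ASMQ shortfall, about 9, is the substantial one. Both rest on two-sided 5%, which the documents do not state for safety. At one-sided 2.5% the shortfalls grow; at one-sided 5% the AL shortfall disappears and the ASMQ pair falls just under 80%.

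The stated figure is a method mismatch, not a miscalculation. The combined Africa and Asia claim is unaffected.

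**What to change.** No extra enrolment is needed. In Protocol 15.1 and SAP 2.2.1, replace the Africa-only sentence with one that names the test, the alpha and the pair, for example:

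> With full enrolment in Africa, Fisher's exact test at two-sided 5% has about 78% power (AL pair, 576 vs 1152) and about 71% power (ASMQ pair, 504 vs 1008) to detect a rise in adverse event incidence from 1% with ACT to 3% with the matching TACT.

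If the present figure is also kept, label it with its method: unpooled normal approximation, two-sided 5%, 87% and 82%. If a different alpha is intended for the safety comparisons, state it in Protocol 15.2.4 and SAP 3.4 and quote the power at that level.

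Add the combined DeTACT-Africa and DeTACT-Asia statement to SAP 2.2.1 with its Fisher power, about 93% (AL) and 88% (ASMQ).

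The cost is wording in two sections and a less favourable Africa-only figure. The analysis and the decision rules stay as they are.
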